9.4.5 PK/PD relationships

[illegible]

9.5 Exploratory endpoint(s)/estimand(s) analysis

CCI

CCI

9.6 (Other) Safety analyses

Not applicable.

9.7 Interim analyses

Data Reviews and dose modifications between each part will be conducted by reviewing available data as described in [Section 4.4](#) and [Section 6.5](#).

Interim analyses are planned for the monitoring of safety data and will be performed approximately after each cohort during the course of the study.

The decision to continue to Part B of the study will be made by the Sponsor and the DMC. If notable adverse events or safety concerns are found at one of the planned dose levels in Part A, the planned dose level in Part B may be adjusted.

CCI

9.8 Sample size calculation

9.8.1 Primary endpoint(s)

CCI

9.8.2 Secondary endpoint(s)

10 Supporting documentation and operational considerations

10.1 Regulatory, ethical, and study oversight considerations

10.1.1 Regulatory and ethical considerations

This study will be conducted in accordance with the protocol and with the following:

- Consensus ethical principles derived from international guidelines including the Declaration of Helsinki and Council for International Organizations of Medical Sciences (CIOMS) international ethical guidelines
- Applicable ICH Good Clinical Practice (GCP) guidelines

- Applicable laws and regulations

The protocol, protocol amendments, ICF, Investigator's Brochure, and other relevant documents (e.g., advertisements) must be submitted to an IRB/IEC by the investigator and reviewed and approved by the IRB/IEC before the study is initiated.

Any amendments to the protocol will require IRB/IEC approval before implementation of changes made to the study design, except for changes necessary to eliminate an immediate hazard to study patients.

Protocols and any substantial amendments/modifications to the protocol will require health authority approval prior to initiation except for changes necessary to eliminate an immediate hazard to study patients.

The investigator will be responsible for the following:

- Signing a protocol signature page confirming his/her agreement to conduct the study in accordance with these documents and all of the instructions and procedures found in this protocol and to give access to all relevant data and records to Novartis monitors, auditors, Novartis Quality Assurance representatives, designated agents of Novartis, IRBs/IECs, and regulatory authorities as required
- Providing written summaries of the status of the study to the IRB/IEC annually or more frequently in accordance with the requirements, policies, and procedures established by the IRB/IEC
- Notifying the IRB/IEC of SAEs or other significant safety findings as required by IRB/IEC procedures
- Providing oversight of the conduct of the study at the site and adherence to requirements of 21 CFR, ICH guidelines, the IRB/IEC, and all other applicable local regulations
- Inform Novartis immediately if an inspection of the clinical site is requested by a regulatory authority

This clinical study was designed and shall be implemented, executed and reported in accordance with the ICH Harmonized Tripartite Guidelines for Good Clinical Practice, with applicable local regulations, and with the ethical principles laid down in the Declaration of Helsinki.

10.1.2 Informed consent process

The investigator or his/her representative will explain the nature of the study, including the risks and benefits, to the patient or their legally authorized representative and answer all questions regarding the study.

Patients must be informed that their participation is voluntary. Patients or their legally authorized representatives will be required to sign a statement of informed consent that meets the requirements of 21 CFR 50, local regulations, ICH guidelines, privacy and data protection requirements, where applicable, and the IRB/IEC or study center.

Informed consent must be obtained before conducting any study-specific procedures (e.g., all of the procedures described in the protocol). The process of obtaining informed consent must be documented in the patient source documents.

The medical record must include a statement that written informed consent was obtained before the patient was enrolled in the study and the date the written consent was obtained. The authorized person obtaining the informed consent must also sign the ICF.

A copy of the ICF(s) must be provided to the patient or their legally authorized representative.

A patient who is rescreened is not required to sign another ICF if the rescreening occurs within 6 hours from the previous ICF signature date. The ICF will contain a separate section that addresses the use of remaining mandatory samples for optional additional research. The investigator or authorized designee will explain to each patient the objectives of the additional research. Patients will be told that they are free to refuse to participate and may withdraw their consent at any time and for any reason during the storage period. A separate signature will be required to document a patient's agreement to allow any remaining specimens to be used for additional research. Patients who decline to participate in this optional additional research will document this.

Eligible patients may only be included in the study after providing (witnessed, where required by law or regulation), IRB/IEC-approved informed consent.

If applicable, in cases where the patient's representative(s) gives consent (if allowed according to local requirements), the patient must be informed about the study to the extent possible given his/her level of understanding. If the patient is capable of doing so, he/she must indicate agreement by personally signing and dating the written informed consent document or separate assent form.

Information about common side effects already known about the investigational treatment can be found in the Investigator's Brochure (IB) (or Core Data Sheet for marketed drugs). This information will be included in the patient informed consent and should be discussed with the patient upon obtaining consent and also during the study as needed. Any new information regarding the safety profile of the investigational drug that is identified between IB updates will be communicated as appropriate, for example, via an Investigator notification or an aggregate safety finding. New information might require an update to the informed consent and then must be discussed with the patient.

The following informed consents are included in this study:

- Main study consent, which also includes:
 - A subsection that requires a separate signature for the 'Optional Consent for Additional Research' to allow future research on data/samples collected during this study
- As applicable, Pregnancy Outcomes Reporting Consent for female patients or the female partners of any male patients who took study treatment
- Patient information sheet for female partners of any male patient who took study treatment
- CCI

CCI

CCI

10.1.3 Data protection

Patients will be assigned a unique identifier by Novartis. Any patient records or datasets that are transferred to Novartis will contain the identifier only; patient names or any information which would make the patient identifiable will not be transferred.

The patient must be informed that his/her personal study-related data will be used by Novartis in accordance with local data protection law. The level of disclosure must also be explained to the patient who will be required to give consent for their data to be used as described in the informed consent.

The patient must be informed that his/her medical records may be examined by Clinical Quality Assurance auditors or other authorized personnel appointed by Novartis, by appropriate IRB/IEC members, and by inspectors from regulatory authorities.

Novartis has appropriate processes and policies in place to handle personal data breaches according to applicable privacy laws.

10.1.4 Committees Structure

10.1.4.1 Data monitoring committee

This study will include a data monitoring committee (DMC) which will function independently of all other individuals associated with the conduct of this clinical trial, including the site Investigators participating in the study. The DMC will review the available clinical trial data in the following situations:

- To decide on the transition of an agent between study Parts
- Planned IAs and unplanned IAs
- If study stopping criteria are met

Specific details regarding composition, responsibilities, data monitoring, meeting frequency, and documentation of DMC reports, minutes, and recommendations will be described in a separate charter that is established between Novartis and the DMC.

10.1.5 Data quality assurance

Monitoring details describing strategy, including definition of study critical data items and processes (e.g., risk-based initiatives in operations and quality such as risk management and mitigation strategies and analytical risk-based monitoring), methods, responsibilities, and requirements, including handling of noncompliance issues and monitoring techniques (central, remote, or on-site monitoring) are provided in the monitoring plan.

Records and documents, including signed ICFs, pertaining to the conduct of this study must be retained by the investigator for 15 years after study completion unless local regulations or institutional policies require a longer retention period. No records may be destroyed during the

retention period without the written approval of Novartis. No records may be transferred to another location or party without written notification to Novartis.

10.1.5.1 Data collection

All data should be recorded, handled, and stored in a way that allows its accurate reporting, interpretation, and verification.

Designated investigator staff will enter the data required by the protocol into the Electronic Case Report Forms (eCRF). The eCRFs have been built using fully validated secure web-enabled software that conforms to 21 CFR Part 11 requirements, investigator site staff will not be given access to the EDC system until they have been trained. Automatic validation programs check for data discrepancies in the eCRFs, allow modification and/or verification of the entered data by the investigator staff.

The investigator/designee is responsible for assuring that the data (entered into eCRF) is complete, accurate, and that entry and updates are performed in a timely manner. The Investigator must certify that the data entered are complete and accurate.

After final database lock, the investigator will receive copies of the patient data for archiving at the investigational site.

All data should be recorded, handled, and stored in a way that allows its accurate reporting, interpretation, and verification.

10.1.5.2 Database management and quality control

Novartis personnel (or designated CRO) will review the data entered by investigational staff for completeness and accuracy. Electronic data queries stating the nature of the problem and requesting clarification will be created for discrepancies and missing values and sent to the investigational site via the EDC system. Designated investigator site staff are required to respond promptly to queries and to make any necessary changes to the data.

Concomitant treatments and prior medications entered into the database will be coded using the World Health Organization (WHO) Drug Reference List, which employs the Anatomical Therapeutic Chemical classification system. Medical history/current medical conditions and adverse events will be coded using the Medical Dictionary for Regulatory Activities (MedDRA) terminology.

Dates of screenings, randomizations, screen failures and study completion, as well as randomization codes and data about all study treatment (s) dispensed to the patient and all dosage changes will be tracked using an Interactive Response Technology (IRT). The system will be supplied by a vendor, who will also manage the database. The data will be sent electronically to Novartis (or a designated CRO) at specific timelines.

Each occurrence of a code break via IRT will be reported to the clinical team and monitor. The code break functionality will remain available until study shut down or upon request of Novartis.

Once all the necessary actions have been completed and the database has been declared to be complete and accurate, it will be locked and made available for data analysis. Any changes to

the database after that time can only be made after written agreement by Novartis development management.

10.1.6 Source documents

Source documents provide evidence for the existence of the patient and substantiate the integrity of the data collected. Source documents are filed at the investigator's site.

Data reported on the CRF or entered in the eCRF that are transcribed from source documents must be consistent with the source documents or the discrepancies must be explained. The investigator may need to request previous medical records or transfer records, depending on the study. Also, current medical records must be available.

The investigator must give the monitor access to all relevant source documents to confirm their consistency with the data capture and/or data entry. The investigator must also keep the original informed consent form signed by the patient (a signed copy is given to the patient). Definition of what constitutes source data and its origin can be found in the clinical trial agreement.

The investigator must maintain accurate documentation (source data) that supports the information entered in the CRF. Study monitors will perform ongoing source data verification to confirm that data entered into the CRF by authorized site personnel are accurate, complete, and verifiable from source documents; that the safety and rights of patients are being protected; and that the study is being conducted in accordance with the currently approved protocol and any other study agreements, ICH GCP, and all applicable regulatory requirements.

Key study personnel must be available to assist the field monitor during these visits. Continuous remote monitoring of each site's data may be performed by a centralized Novartis CRA organization. Additionally, a central analytics organization may analyze data & identify risks & trends for site operational parameters, and provide reports to Novartis clinical teams to assist with trial oversight.

10.1.7 Publication policy

The protocol will be registered in a publicly accessible database such as clinicaltrials.gov. In addition, after study completion (defined as last patient last visit) and finalization of the study report the results of this trial will be submitted for publication and posted in a publicly accessible database of clinical trial results, such as the Novartis clinical trial results website and all required health authority websites (e.g., Clinicaltrials.gov).

For details on the Novartis publication policy including authorship criteria, please refer to the Novartis publication policy training materials that were provided to you at the trial investigator meetings.

Any data analysis carried out independently by the investigator should be submitted to Novartis before publication or presentation.

Summary results of primary and secondary endpoints will be disclosed based upon the global Last Patient Last Visit (LPLV) date, since multinational studies are locked and reported based upon the global LPLV.

10.1.8 Protocol adherence and protocol amendments

This protocol defines the study objectives, the study procedures and the data to be collected on study patients. Additional assessments required to ensure safety of patients should be administered as deemed necessary on a case-by-case basis. Under no circumstances including incidental collection is an investigator allowed to collect additional data or conduct any additional procedures for any purpose involving any investigational drugs under the protocol, other than the purpose of the study. If despite this interdiction prohibition, data, information, observation would be incidentally collected, the investigator shall immediately disclose it to Novartis and not use it for any purpose other than the study, except for the appropriate monitoring on study patients.

Investigators ascertain they will apply due diligence to avoid protocol deviations. If an investigator feels a protocol deviation would improve the conduct of the study this must be considered a protocol amendment, and unless such an amendment is agreed upon by Novartis and approved by the IRB/IEC and health authorities, where required, it cannot be implemented.

10.1.8.1 Protocol amendments

This study uses a platform type design with the potential to investigate multiple therapies in the context of a single disease. Each time a new agent is introduced, agent-specific information will be added to the protocol as a substantial amendment and submitted to Health Authorities and Ethical Committees, as required by local regulations.

Any change or addition to the protocol can only be made in a written protocol amendment that must be approved by Novartis, health authorities where required, and the IRB/IEC prior to implementation.

Only amendments that are required for patient safety may be implemented immediately provided the health authorities are subsequently notified by protocol amendment and the reviewing IRB/IEC is notified.

Notwithstanding the need for approval of formal protocol amendments, the investigator is expected to take any immediate action required for the safety of any patient included in this study, even if this action represents a deviation from the protocol. In such cases, Novartis should be notified of this action and the IRB/IEC at the study site should be informed according to local regulations.

11 Appendices

11.1 Appendix 1: Liver Safety Monitoring

Liver safety monitoring

To ensure patient safety and enhance reliability in determining the hepatotoxic potential of an investigational drug, a standardized process for identification, monitoring and evaluation of liver events has to be followed.

Once a patient is exposed to study treatment, every liver event defined in [Table 11-1](#) should be followed up by the investigator or designated personnel at the trial site, as summarized below. Additional details on actions required in case of liver events are outlined in [Table 11-2](#) and [Table 11-3](#). Repeat liver chemistry tests (i.e., ALT, AST, TBL, PT/INR, ALP and G-GT) to confirm elevation.

- These liver chemistry repeats will be performed a local laboratory to monitor the safety of the patient. If a liver event is subsequently reported, any local liver chemistry tests previously conducted that are associated with this event should have results recorded on the appropriate CRF.
- If the initial elevation is confirmed, close observation of the patient will be initiated, including consideration of treatment interruption if deemed appropriate.
- Discontinuation of the investigational drug (refer to [Section 7](#) Discontinuation of study treatment section), if appropriate
- Hospitalization of the patient if appropriate
- Causality assessment of the liver event
- Thorough follow-up of the liver event should include
 - Based on investigator's discretion: serology tests, imaging and pathology assessments, hepatologist's consultancy; obtaining more detailed history of symptoms and prior or concurrent diseases, history of concomitant drug use, exclusion of underlying liver disease

All follow-up information and procedures performed must be recorded as appropriate in the CRF.

Potential Hy's Law cases (defined as ALT or AST $> 3 \times$ ULN and Total bilirubin $> 2 \times$ ULN [mainly conjugated fraction] without notable increase in ALP to $> 2 \times$ ULN) need to be reported as SAE to Novartis within 24 hrs.

CCI

CCI

CCI

CCI

CCI

12 Cohort Specific Information

This section contains details that pertain to specific cohorts and anti-malarial agents and should be considered as supplementary to information presented in the preceding core protocol sections and respective Investigator Brochures. If there are no treatment-specific details presented for a given topic (e.g., cohort- or treatment-specific eligibility criteria, study restrictions, food effects, etc.), then the information in the corresponding section in the core protocol for that topic should be implemented without further adjustment.

12.1 Cohort A1: INE963

CCI

12.1.1 INE963 Background

CCI

12.1.2 Cohort A1 Study Design

As mentioned in [Section 3](#), this is a multi-part platform study. Part A evaluates anti-malarial agents as monotherapy, and Part B evaluates anti-malarial agents as combination therapy

In Cohort A1, patients will receive a single dose of INE963.

CCI

CCI

12.1.4 Cohort A1 Risks and Benefits

INE963 is expected to reduce the number of circulating malaria parasites in the blood of patients and consequently improve their clinical symptoms.

INE963 IMP Related Risk

Against the background of the COVID-19 pandemic, the potential risk of a patient developing COVID-19 has been considered in terms of the risk-benefit evaluation. The mode of action of this anti-malarial agent has been considered alongside available pre-clinical and clinical data (including class effects) and it is considered that a patient would not be at increased risk of either becoming infected with severe acute respiratory syndrome coronavirus 2 (SARS-CoV-2; the virus that causes COVID-19) or experiencing a more severe illness. That is, this agent has no known immunomodulatory effect that would confer an increased risk to patients enrolled in the study.

12.1.5 Cohort A1 Study Population and Special Restrictions

Additional Exclusion Criteria

Patients meeting any of the following criteria are not eligible for inclusion in this cohort:

Women of child-bearing potential, defined as all women physiologically capable of becoming pregnant, unless they are using highly effective methods of contraception during dosing and for 5 half-lives. Highly effective contraception methods include:

- Total abstinence when this is in line with the preferred and usual lifestyle of the subject. Periodic abstinence (e.g., calendar, ovulation, symptothermal, post-ovulation methods) and withdrawal are not acceptable methods of contraception.
- Female bilateral tubal ligation, female sterilization (have had surgical bilateral oophorectomy with or without hysterectomy), or total hysterectomy at least six weeks before taking investigational drug. In case of oophorectomy alone, only when the reproductive status of the woman has been confirmed by follow up hormone level assessment.
- Male sterilization (at least 6 months prior to screening). For female patients on the study, the vasectomized male partner should be the sole partner for that patient.

- Use of oral (estrogen and progesterone), injected, or implanted hormonal methods of contraception or placement of an intrauterine device (IUD) or intrauterine system (IUS) or other forms of hormonal contraception that have comparable efficacy (failure rate < 1%), for example hormone vaginal ring or transdermal hormone contraception. Coartem/Riamet may reduce the effectiveness of hormonal contraceptives. Therefore, patients randomized to Coartem using oral, transdermal patch, or other systemic hormonal contraceptives should be advised to use an additional non-hormonal method of birth control.
- In case of use of oral contraception, women should have been stable on the same pill for a minimum of 3 months before taking investigational drug.

[figure not shown]

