4.3 Rationale for choice of control drugs (comparator) or combination drugs

Choice of control drug

There is a control treatment only in Part B. The control treatment used in Part B of this study is Coartem, the artemisinin-based combination therapy artemether-lumefantrine. Coartem is widely used for *P. falciparum* malaria and has a well-characterized safety and efficacy profile ([Hamed, Grueninger 2012](#)). For these reasons, Coartem is considered the appropriate comparator treatment for this study.

Choice of combination drug(s)

This study is designed to test a number of different investigational anti-malarial agents (Part A) or combinations of anti-malarial agents (Part B). Agents must meet pre-specified criteria as outlined in [Section 3.1](#) to be included in the study. In some cases, an investigational anti-malarial agent may also be combined with a marketed one. Each of the candidate agents to be studied will have rationale added in a substantial amendment. Refer to [Section 12](#) for cohort-specific details.

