6.1.2 Treatment arms/group

In Part A, patients will be randomized at the screening visit to receive a single dose of an anti-malarial agent at one of the dose levels at equal ratios.

In Part B, patients will be randomized at the screening visit to receive a single dose of a combination of anti-malarial agents or the standard of care (Coartem).

See [Section 12](#) for cohort specific information.

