6.2.2 Handling of other treatment

The following non-study treatment has to be monitored specifically:

- Coartem or other local standard anti-malarial agent per investigator discretion may be administered as rescue medication in case of treatment failure. Monitoring of rescue medication compliance and drug accountability will be performed by the field monitors during site or remote monitoring visits, and at the completion of the trial.

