6.6 Continued access to study treatment after the end of the study

There will be no study treatment available to patients following the end of the study. This study includes Coartem or other local standard anti-malarial agent administered to all patients in Part A on Day 29 and in case of treatment failure in Part A or B. There are other treatment options for uncomplicated malaria.

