6.8.3 Rescue medication

The following rescue medications may be used per investigator discretion:

- Coartem (Artemether-Lumefantrine)
or
- Other local standard anti-malarial agent

In Part A, Coartem (artemether-lumefantrine) or other local standard anti-malarial agent per investigator discretion will be administered on Day 29 in all patients in Part A of the study. If Coartem or other local standard anti-malarial agent is used as rescue medication prior to Day 29 due to treatment failure (see [Section 8.3.4](#)), then another course is not needed at Day 29.

In Part B, Coartem or other local standard anti-malarial agent per investigator discretion will be used as rescue medication only for patients not randomized to the SoC in Part B if they meet the treatment failure criteria (see [Section 8.3.4](#)). An alternative rescue medication should be used for patients assigned to the SoC arm if they met treatment failure criteria.

Although the use of the above rescue medication is allowable at any time during the study when there is treatment failure in Part A or B, the use of rescue medication should be used at the discretion of the PI following the failure criteria as outlined in [Section 8.3.4](#). The date and time of rescue medication administration as well as the name and dosage regimen of the rescue medication must be recorded.

7 Discontinuation of study treatment and participant discontinuation/withdrawal

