## 5.3 Non-study anti-malarial drugs

**Table 5-6 Non-study anti-malarial drugs (from concomitant medication dataset) with respective ATC codes**

Non-study drug anti-malarial*	ATC code
Aminoquinolines	P01BA
Biguanides	P01BB
Methanolquinoline	P01BC
Diaminopyridimides	P01BD
Artemisinin and derivatives, plain	P01BE
Artemisinin and derivatives, combinations	P01BF
Other Anti-malarial	P01BX

\* Part A: Applies only to patients who took Coartem prior to Day 29 visit.

Additional non-study anti-malarial drugs will be identified by the PD code COMD02 (Concomitant antimicrobial with antimalarial activity).

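### In Cohort A1 the advice to add a non-hormonal contraceptive applies only to patients randomized to Coartem; no A1 patient is, yet A1 patients may be given Coartem on Day 29 or earlier as rescue

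*Protocol*

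**What the plan says.** Section 12.1.5 accepts hormonal methods as highly effective contraception for women in Cohort A1, to be used during dosing and for 5 half-lives. It warns in general terms that Coartem may make hormonal contraceptives less effective. The action that follows is narrower: "Therefore, patients randomized to Coartem using oral, transdermal patch, or other systemic hormonal contraceptives should be advised to use an additional non-hormonal method".

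On who is assigned what, 6.1.2 randomizes Part A patients "to receive a single dose of an anti-malarial agent at one of the dose levels at equal ratios". Section 12.1.2 states: "In Cohort A1, patients will receive a single dose of INE963". Section 4.3 adds: "There is a control treatment only in Part B".

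On who may receive Coartem, 6.8.3 says that Coartem or another local standard antimalarial "will be administered on Day 29 in all patients in Part A of the study". A course already given as rescue for treatment failure makes the Day 29 course unnecessary. Section 6.6 agrees: "This study includes Coartem or other local standard anti-malarial agent administered to all patients in Part A on Day 29". Section 6.2.2 allows the same drugs on treatment failure: "Coartem or other local standard anti-malarial agent per investigator discretion may be administered as rescue medication in case of treatment failure". The SAP also foresees early use, in a footnote to Table 5-6: "Part A: Applies only to patients who took Coartem prior to Day 29 visit".

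**The concern.** The reason given for the advice is exposure to Coartem, but the condition for giving it is randomization to Coartem. In Part B the two largely coincide. In Cohort A1 they separate completely: no one is randomized to Coartem, while every patient is due Coartem or an alternative by Day 29.

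Staff who give Coartem to an A1 woman on a pill, patch or other systemic hormonal method therefore have a warning but, as worded, no instruction to advise a back-up method. What is at stake is a precaution against unintended pregnancy around treatment.

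**Working it through.** The protocol states no figure on this point, so the check is mainly a comparison of sections.

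**1. Who the instruction covers in A1.** The condition is randomization to Coartem. Under 6.1.2, 12.1.2 and 4.3, the A1 arms are dose levels of INE963 with no control. Patients meeting the condition: 0.

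**2. Who may receive Coartem in A1.** Under 6.6 and 6.8.3, all Part A patients receive Coartem or a local alternative on Day 29, unless already rescued. The choice is the investigator's, so exposure to Coartem is possible but not certain for any one patient.

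**3. Whether other legible text fills the gap.** Two places refer staff to the Coartem prescribing information. Section 5.3.1 limits this to patients taking Coartem in Part B. In 6.8.2 the reference sits under a heading for Part B cohorts with a Coartem arm. Neither reaches A1.

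**4. Whether the same wording causes trouble in Part B.** Sections 12.2.6 and 12.3.6 carry the same sentence. There it reaches the Coartem arm and leaves out only combination-arm patients rescued with Coartem. That smaller gap is partly covered by 5.3.1 and 6.8.2. It is real in B2: under 12.3.7, a combination-arm patient who vomits the replacement dose must be given Coartem or another suitable rescue drug, so Coartem can be given near the dosing day without randomization to it.

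**5. When Coartem would fall inside the A1 contraception window.** INE963 is a single dose on Day 1, so the window closes 5 half-lives later. Coartem given *d* days after that dose is inside the window only if the half-life exceeds *d*/5. Day 29 is *d* = 28. Days 8 and 4 (*d* = 7 and 3) are illustrative rescue days. The last Coartem dose is taken as 60 hours (2.5 days) after the first, which assumes the Part B schedule in 12.2.2 (Table 12-9) also applies in Part A.

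| Coartem starts | First dose inside window if half-life exceeds | Whole course inside window if half-life exceeds |
|---|---|---|
| Day 29 | 28/5 = 5.6 d (134 h) | 30.5/5 = 6.1 d (146 h) |
| Day 8 | 7/5 = 1.4 d (34 h) | 9.5/5 = 1.9 d (46 h) |
| Day 4 | 3/5 = 0.6 d (14 h) | 5.5/5 = 1.1 d (26 h) |

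The INE963 half-life is not legible, so these are break-even values only and show no overlap. They do show that the earlier the rescue, the shorter the half-life needed for one.

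**The case against.** The strongest reply is that much of the A1 section cannot be seen. Section 12.2.6 points to 12.1.5 for special restrictions on INE963, yet the legible part of 12.1.5 holds only exclusion criteria. Section 12.1.5.1, on concomitant therapy needing caution, is redacted, and the consent pages were removed. Advice on non-randomized Coartem could be in any of these. This stands as a limit: one cannot say that A1 women go unadvised, only that the legible rule has the wrong scope. Hidden text would not make that scope right.

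Second, the warning and the remedy are adjacent sentences, and sensible staff would connect them. This also stands, and it is why the point is small.

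Third, Coartem in Part A is a discretionary non-study drug, and 6.8.1 already requires each concomitant drug to be assessed against the exclusion criteria and prohibited medications. But that requirement does not mention contraception. The protocol also writes the advice out for randomized Coartem patients, and its reason applies equally to A1 patients given the drug.

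Fourth, no consequence is shown: the half-life and the number of women affected are unknown. That is correct, and none is claimed.

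Finally, the SAP cites protocol version 03 of 20 March 2024, while the latest amendment in the protocol supplied is dated June 2023. The wording may already have changed, which the sponsor can check.

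**Conclusion.** The concern holds as a defect in the scope of a safety instruction. On the legible text the instruction covers 0 Cohort A1 patients, although Coartem is a named option for all of them on Day 29 or earlier as rescue. The sentence reads like shared text that was not adapted to Part A.

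The practical weight is low. It arises only for women on a systemic hormonal method, only if Coartem is chosen over the permitted alternative, and it bears on the required contraception window only if the INE963 half-life is long enough. The number affected is not given and may be zero. There is no effect on sample size, power or any analysis. The change is worth considering because it costs almost nothing.

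**What to change.** In 12.1.5, replace the condition of randomization to Coartem with: *patients who receive Coartem at any time in the study (by randomization, as rescue, or on Day 29 in Part A)*. State that the advice is given when Coartem is dispensed. This timing matters in Part A because Section 8 makes Day 29 the final visit and 3.1 then provides only a safety call on Day 31. Use the same wording in 12.2.6 and 12.3.6 for consistency. How long the extra method is needed is for the sponsor's clinical team to set.

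The cost is one phrase in 12.1.5, repeated in two other cohort sections, with no added visits, tests or patients.
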